## 5. EFFICACY ENDPOINTS

### 5.1 Efficacy Endpoints – Definition

#### Surveillance for respiratory illness – Flu season 2018-2019

- *Active Surveillance:* All subjects were contacted twice a week by a call center starting on November 15th of the vaccination year until the week of March 31th the following year.
- *Passive Surveillance:* All subjects were instructed to contact their study site if they experienced symptoms of a respiratory illness from Day 14 post-second vaccination day until May 15th the following year.

Note: Active surveillance might be extended by the medical monitor for those countries in which influenza does not reach low levels by March 30.

#### Surveillance for respiratory illness – Flu season 2019-2020

- *Active Surveillance:* All subjects will be contacted twice a week by a call center starting on December 1st, 2019 until the week of April 30th.
- *Passive Surveillance:* All subjects will be instructed to contact their study site if they experience symptoms of a respiratory illness from September 15, 2019 to May 15, 2020.

#### Protocol-defined Influenza-Like Illness (ILI)

An ILI episode was identified if at least one respiratory symptom and at least one systemic symptom occurred concurrently; the respiratory symptoms being either

- sore throat,
- cough,

- sputum production,
- nasal discharge or congestion,
- wheezing or difficult breathing

and the systemic symptoms being either

- fever (oral temperature  $>37.2^{\circ}\text{C}$  for age 50-59 years, or  $>36.7^{\circ}\text{C}$  for age 60 years or more, or increased  $\geq 1.3^{\circ}\text{C}$  from baseline),
- headache,
- myalgia and/or arthralgia,
- chills,
- fatigue (tiredness for at least 12 hours).

The time of onset for an ILI episode is defined as the time from 14 days after the second vaccination to the date when at least one respiratory symptom and at least one systemic symptom occurred concurrently. For subjects who received only one vaccination, the time of onset for the ILI episode will be defined from 35 days after first vaccination. New episodes of ILI are defined as occurring at least 14 days after the end of a previous episode.

The duration of the ILI episode (days) is defined as follows: last stop date of ILI symptoms for the episode - onset date of the ILI episode + 1.

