Protocol defined ILI end date is the date when for at least 24 hours ILI symptoms are no longer present. Of note, some symptoms may persist after ILI for a long time, but the duration of ILI is to be determined by presence of symptoms of ILI understood as active disease, or “influenza symptom”, contrary to symptoms being part of an underlying chronic condition (e.g. COPD, arthritis), and contrary to chronic complications and/or sequelae of the ILI. When no clear end of ILI can be observed, the PI is requested to make rational judgment and determine the ILI end date based on available data and his/her experience. It is expected, that normally, ILI should not last longer than 2-3 weeks, and in case of suspected overlapping new infection, the two infection episodes should be recognized by PI as separate ILI cases.

Laboratory testing for the confirmation of influenza:

All NP/nasal and throat swab specimens will be submitted for analysis by polymerase chain reaction (qRT-PCR), and when the result is found positive, and if there is a sufficient content of viruses (as determined by Ct value ≤ 35)” [Ct= cycle threshold] another aliquot from such specimen will be also examined by culture confirmation test. Typing and subtyping of the influenza virus will be performed with PCR based method.

Optional test: Positive cultures samples will be stored and may undergo additional testing in the future (subtyping or strain identification, utilizing genetic sequencing and antigenic analysis using hemagglutination inhibition [HAI] against a panel of known standard ferret reference antisera to different viral strains) to further determine the breadth of protection provided by M-001.

Out of study influenza infection confirmation: in cases when no swab collection was performed within study framework, but valid, relevant external medical documentation exists confirming recent or ongoing influenza infection (laboratory confirmation – PCR, culture or serology - IgM antibodies), such medical documentation will be subject to sponsor’s approval as surrogate proofs of influenza infection, and if approved as valid, may be taken into account for exploratory analyzes. Details of exploratory analyzes will be defined in statistical analysis plan.

7.4. Safety Follow Up Visit, Visit 4, Day 202: Phone Call/ Electronic Communication (180 days [+/-14 days] post last study vaccination day)

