### **Confirmed influenza in association with protocol-defined ILI**

A subject is said to have a laboratory-confirmed influenza in association with protocol-defined ILI, if

- the subject had a protocol-defined ILI;
- the subject had a nasopharyngeal (NP) or nasal and throat swab; and
- the NP or nasal and throat swab was qRT-PCR- or culture-positive for influenza of any type.

A subject is said to have a culture-confirmed influenza in association with protocol-defined ILI if

- the subject had a protocol-defined ILI;
- the subject had a NP or nasal and throat swab; and
- the NP or nasal and throat swab was culture positive for influenza of any type.

Although the protocol required the nasal or throat swab to be performed during a window of 3 days post onset date, positive results from nasal or throat swabs obtained out of the window of 3 days will be used in the analysis and the subject will be considered as having laboratory confirmed influenza.

Number of subjects with missing swab results will be reported. The number of swabs performed out of the window of 3 days post onset date will be reported.

The time to onset and duration of the confirmed case of influenza with protocol-defined ILI will be identical to the time to onset and duration of the associated ILI episode.

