Descriptive statistics of  $p_V = C_V / N_V$  and  $p_P = C_P / N_P$  by country and site within country will be provided,  $N_V$  et  $N_P$  being the number of subjects and  $C_V$  and  $C_P$  being the number of cases, within each country, and site within country.

Sensitivity analyses for the primary efficacy endpoint:

Time to first qRT-PCR- or culture-confirmed influenza in association with a protocol-defined ILI will be considered.

For this analysis, performed on the PP set, the following proportional hazard model will be fitted:

$$h(t) = h_0(t) \exp[\beta_1 \text{ Group}]$$

where  $h_0(t)$  is the baseline hazard function, Group is the treatment variable, (0 for placebo and 1 for M-001), and  $\beta_1$  is the group effect.

The proportional hazard model assumes that the ratio of the hazard functions associated with M-001 and placebo is constant over time.

Under this model, the VE between M-001 and placebo is estimated by  $100(1 - e^{\beta_1})$  and its associated 95% CI will be derived as  $100(1 - e^{\beta_1 \pm z_{0.975} \text{sterr}(\beta_1)})$ , where  $\text{sterr}$  and  $z_{0.975}$  represents the standard error and 97.5% quantile for the normal distribution, respectively.

The p-value resulting from the test of  $H_0: \beta \geq \ln(0.6)$  versus  $H_a: \beta < \ln(0.6)$  will be reported (test will be performed at the one-sided level 0.025).

In addition, the time to first qRT-PCR- or culture-confirmed influenza in association with a protocol-defined ILI will be presented using a Kaplan-Meier plot, with x-axis values at 30, 60, 90, 120, 150, 180, 210 and 240 days.

For the time-to-event analysis, the time of the first qRT-PCR or culture confirmed influenza in association with a protocol-defined ILI is the time of the first symptom associated with the ILI episode. This time will be calculated in days from the start of the surveillance period (14 days post second vaccination). Subjects without qRT-PCR- or culture-confirmed influenza will be censored at the last successful contact and the associated time in the analysis will be the number of days from the start of the surveillance period (14 days post second vaccination) until censoring time. For the ITT analysis, subjects with no surveillance contact will be censored at day 1.

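### The SAP's 14-day rule for a new ILI episode departs from the protocol and can back-date and lengthen a confirmed influenza that follows another ILI

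*SAP*

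**What the plan says.** SAP 5.1, on protocol-defined ILI: "New episodes of ILI are defined as occurring at least 14 days after the end of a previous episode". The clock runs from the end of the previous episode, and a second illness with a different swab result is not exempted. The same subsection sets episode duration as "last stop date of ILI symptoms for the episode - onset date of the ILI episode + 1".

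The next subsection, on confirmed influenza, says that the onset and duration of a confirmed case "will be identical to the time to onset and duration of the associated ILI episode". In SAP 5.4.2 the event time for the Cox and Kaplan-Meier analyses "is the time of the first symptom associated with the ILI episode".

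Protocol 7.3, under ILI follow-up calls, works differently. It says "Protocol defined ILI end date is the date when for at least 24 hours ILI symptoms are no longer present", and "in case of suspected overlapping new infection, the two infection episodes should be recognized by PI as separate ILI cases". It expects that normally "ILI should not last longer than 2-3 weeks". It sets no minimum gap between two ILIs.

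SAP 3.2 adds a third rule. For the second secondary outcome, resolution is the first time at which every listed symptom and fever have gone and stay away for at least one day.

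SAP section 11 lists the changes from protocol version 5.0. The 14-day rule is not among them, nor is it in the SAP's opening summary of changes.

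**The concern.** Sites working to the protocol may record and swab two ILIs that the SAP does not count as two episodes. If the first is a swab-negative cold and the second, starting less than 14 days after the cold ended, is PCR-positive influenza, the confirmed case needs an onset and a duration. The only episode the SAP recognises began with the cold.

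Three things are exposed:

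- **Second secondary endpoint.** It is analysed only among confirmed cases, in bands of days with symptoms, so a wrong start date can move a subject to another band.
- **Cox and Kaplan-Meier analyses.** The event time moves back to the first symptom of the earlier illness.
- **Supplementary ILI episode count and Poisson rate.** Two recorded illnesses count as one.

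**Working it through.** The plan states no figure that depends on this rule, so there is nothing to reproduce. The check applies both sets of rules to the same timelines.

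**Formulas.** Let d1 be the length of the first illness, g the number of days from its last day to influenza onset, and d2 the length of the influenza. For g below 14, on the reading that the later illness belongs to the earlier episode:

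- back-dating = d1 + g − 1
- SAP 5.1 duration = last stop − first onset + 1 = d1 + g − 1 + d2

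Under the protocol the two illnesses stay separate. Back-dating is 0 and duration is d2.

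**Illustration.** Cold on days 1 to 7, symptom-free on days 8 to 15, influenza on days 16 to 23. Here d1 = 7, g = 16 − 7 = 9 and d2 = 8.

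- Protocol: onset day 16, duration 23 − 16 + 1 = 8 days, band 7 to under 14.
- SAP 5.1: onset day 1, so 7 + 9 − 1 = 15 days early; duration 23 − 1 + 1 = 23 days, top band.
- SAP 3.2 resolution rule applied to the same joined episode: it ends with the cold after day 7. The result is 7 days, none of them influenza.

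**Wider set.** With d2 = 7, d1 of 3, 5, 7 or 10 and g of 1, 4, 7 or 13, there are 16 timelines. Back-dating runs from 3 + 1 − 1 = 3 days to 10 + 13 − 1 = 22 days. Duration runs from 10 to 29 days against 7. The band changes in 13 of the 16. The three that keep their band are d1 = 3 with g = 1 (10 days), d1 = 3 with g = 4 (13 days) and d1 = 5 with g = 1 (12 days).

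**Does the case survive?** A swab on the first day of influenza in the illustration is 15 days after the joined episode's onset, outside the 3-day window. SAP 5.1 nevertheless says "positive results from nasal or throat swabs obtained out of the window of 3 days will be used in the analysis", so the subject remains a confirmed case.

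**How many cases.** The documents give no ILI rate. Assume r non-influenza ILIs per subject over a season of L days, at a constant rate and independent of influenza. The share of confirmed cases preceded by an ILI that ended within w days is 1 − exp(−r × w / L), applied to the planned 182 cases:

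| r per season | w = 13, L = 180 | w = 14, L = 150 |
|---|---|---|
| 0.1 | 0.7%, about 1 case | 0.9%, about 2 cases |
| 0.5 | 3.6%, about 6 cases | 4.6%, about 8 cases |
| 1.0 | 7.0%, about 13 cases | 8.9%, about 16 cases |

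**The case against.** Much of the case on the other side stands.

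- **Primary endpoint.** A reader might infer that primary case status is left to the analyst, or that cases are lost. The documents do not support this. SAP 5.1 defines a confirmed case at subject level (an ILI, a swab, a positive result) and accepts late positives. The one possible exception is an earlier ILI that began before surveillance opened 14 days after the second dose. The back-dated onset could then fall outside the window in SAP 5.2.
- **Third secondary endpoint.** A reader might also infer that this changes. Its main analysis is the proportion of subjects with ILI, and a subject with a cold and then influenza counts once under either rule. Only the additional episode count and Poisson rate can move.
- **Merging is an inference.** The SAP says when an episode is new; it does not say where the symptoms of a non-new illness go. Joining them to the earlier episode is the ordinary reading. The other reading leaves the influenza with no episode to supply its onset and duration. Both leave the SAP needing a sentence.
- **Inflated duration is not certain.** SAP 3.2 would end the joined episode with the cold, and symptom-free days are not days with symptoms. This shows that the SAP's own rules disagree; it does not make any of the results correct for the influenza.
- **No bias between arms is shown.** The rule is the same in both arms, Cox is a sensitivity analysis, and no effect on a hazard ratio or on VE has been computed.
- **The protocol text is recording guidance, and section 11 says the SAP gives more detail than the protocol.** This is fair for a convention on which the protocol is silent. It is weaker for a rule that can undo the protocol's instruction to keep infections separate.

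**Conclusion.** The contradiction is real and undeclared. Protocol 7.3, SAP 3.2 and SAP 5.1 can give different durations for the same confirmed influenza. On the ordinary reading of SAP 5.1, an influenza starting less than 14 days after the end of another ILI is back-dated and lengthened: 23 days against 8, and 15 days early, in the illustration.

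The reach is limited to the duration bands of the second secondary endpoint, the event times in the time-to-event sensitivity analyses, and the supplementary ILI episode count and rate. The primary VE count and the proportion of subjects with ILI are largely unaffected, apart from the possible exception before surveillance opened.

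The share of cases is probably small, about 1 to 16 of 182. That range rests wholly on the assumed ILI rates, a season of 150 to 180 days, and independence of successive illnesses.

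**What to change.** In SAP 5.1:

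- Take onset, stop date and duration of a confirmed case from the investigator-recorded ILI to which the first positive swab belongs.
- For this purpose, treat ILIs that the investigator recorded as separate infections as separate.
- Keep any 14-day rule only for counting ILI episodes or repeat positives, and say so.

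Reconcile protocol 7.3, SAP 3.2 and SAP 5.1 on when an illness ends. List the resulting rule in SAP section 11.

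A general 24-hour reset for all ILI counts is not proposed. Protocol 7.3 allows for symptoms that recur, and such a reset could split one relapsing illness into two.

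The cost is SAP wording and programming before unblinding. No new data are needed, because the ILI records and swab results are already collected.

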### Secondary efficacy assessment:

1. Vaccine efficacy against culture-confirmed influenza illness, defined as  $VE^c = 1 - [p_V^c/p_P^c]$ , where  $p_V^c$  and  $p_P^c$  are the proportions of subjects with culture-confirmed influenza in association with a protocol-defined Influenza-Like Illness (ILI) in the M-001 experimental and placebo groups, respectively.
2. Average duration of the ILI episode or average number of days with respiratory or systemic symptoms during the first qRT-PCR- or culture-confirmed influenza illness episode in the M-001 experimental group and placebo group.
3. Proportion of subjects with ILI episodes in the M-001 experimental group and placebo group.

For the primary efficacy and secondary assessments 1 and 2 in case of multiple qRT-PCR- or culture-confirmed ILI events observed for the same subject, only the first qRT-PCR- or culture-confirmed ILI event will be considered. For the secondary assessment 3, the number of ILI episodes in the M-001 experimental group and placebo group will also be assessed.

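### SAP 5.1 and SAP 5.4.2 date a confirmed influenza case differently, and the SAP does not say from which date the symptom-days endpoint is counted

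*SAP*

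**What the plan says.** **Onset and duration of an episode.** SAP 5.1, under the ILI definition, takes as onset "the date when at least one respiratory symptom and at least one systemic symptom occurred concurrently". Episode duration is "last stop date of ILI symptoms for the episode - onset date of the ILI episode + 1".

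**Confirmed cases.** SAP 5.1, under confirmed influenza, says that the time to onset and duration of a confirmed case "will be identical to the time to onset and duration of the associated ILI episode".

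**Time-to-event analysis.** SAP 5.4.2, under the sensitivity analyses, sets a different date. For the Cox and Kaplan-Meier analyses only, the event date of such a case "is the time of the first symptom associated with the ILI episode". Time is counted in days from 14 days after the second vaccination.

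**Secondary endpoint 2.** Protocol 3.2.2 and SAP 2.2, 3.2 and 5.4.2 describe it as days on which a respiratory or a systemic symptom is present during the first confirmed episode. SAP 5.2 introduces it as "Average duration of the ILI episode or average number of days with respiratory or systemic symptoms". SAP 5.4.2 then puts the number of days into four bands with cut-points at 7, 14 and 21 days. It compares the arms with a Cochran-Mantel-Haenszel test and does not cite the SAP 5.1 formula. The planned outputs (Tables 14.2.23.1 and 14.2.23.2) are titled as a duration of ILI symptoms.

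**The concern.** There are two separate problems.

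First, when the two symptom types start on different days, SAP 5.1 and SAP 5.4.2 give a confirmed case two different times to onset. Two programmers could each follow the SAP and build different Cox and Kaplan-Meier datasets. In the Cox analysis, a case could also fall before time zero.

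Second, the symptom-days endpoint is worded with *or*, while the only duration formula starts at an *and* date. SAP 5.1 assigns that formula to confirmed cases and SAP 5.2 names episode duration as one form of the endpoint. A programmer could therefore reasonably band the SAP 5.1 duration. The days between the first symptom and coincidence would then be left out, and some cases would fall into a lower band than the endpoint's wording implies.

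**Working it through.** **The plan's own figure.** The documents give no sample size, standard deviation or power for the symptom-days endpoint. The nearest figure is the planned 182 confirmed cases (SAP 3.4), roughly the number of cases that would be banded. It reproduces:

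- Expected cases: 12,000 × 0.9 / 2 = 5,400 per arm. Reading 2.41% as the placebo attack rate, 5,400 × 0.0241 × (1 + 0.38) = 179.6.
- Exact conditional test: the null share of cases in the vaccine arm is 0.6/1.6 = 0.375, and at VE 62% it is 0.38/1.38 = 0.2754. With 182 cases the criterion is met at 55 or fewer vaccine cases, with power 81.5% against the stated 80%.

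**Time to onset.** Take a subject with cough from day 13 after dose 2 and fever from day 15.

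- SAP 5.1: the episode qualifies on day 15, so time to onset is 15 − 14 = +1. The event meets the 14-day rule in SAP 5.2 and counts in the primary VE.
- SAP 5.4.2: the first symptom is on day 13, so the event time is 13 − 14 = −1.

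The SAP has no rule for a negative time. An event before time zero must be dropped from the Cox fit or altered, so the Cox and primary case counts can differ. The window is only as long as the lag between symptom types, and SAP 3.4 places vaccination before the influenza season starts. Few such cases are expected.

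**Symptom days.** Days lost under the SAP 5.1 formula = date of coincidence − date of first symptom. This is zero when both types start together and is never negative. Assuming symptoms without gaps:

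| First symptom | Coincidence | Last stop | From first symptom | SAP 5.1 formula |
|---|---|---|---|---|
| day 1 | day 3 | day 8 | 8 (band 7 to <14) | 8 − 3 + 1 = 6 (band <7) |
| day 1 | day 3 | day 10 | 10 (band 7 to <14) | 8 (band 7 to <14) |
| day 1 | day 4 | day 15 | 15 (band 14 to <21) | 12 (band 7 to <14) |
| day 1 | day 1 | day 8 | 8 (band 7 to <14) | 8 (band 7 to <14) |

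Only cases with staggered onset lose days, and only those that cross a cut-point change band.

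**How many might move.** The documents give neither lags nor durations, so every input here is an assumption. Durations were simulated as log-normal (log-SD 0.5, rounded to whole days), with a fixed lag in a given share of cases. Share of cases that drop a band:

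| Lag, share of cases with it | Median 7 days | Median 10 days | Median 14 days |
|---|---|---|---|
| 1 day, 25% | 3.4% | 3.6% | 3.2% |
| 1 day, 100% | 13.9% | 14.6% | 12.8% |
| 2 days, 50% | 12.8% | 14.2% | 12.9% |
| 3 days, 100% | 34.9% | 41.2% | 38.8% |

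The range is about 3% to 41%, or about 6 to 75 of 182 cases. With 7-day bands, the share moved is roughly the mean days lost divided by 7. For example, a 2-day lag in half the cases loses 1.0 day on average, and 1/7 = 14.3% against a simulated 14.2% at median 10.

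**The case against.** The strongest reply is that SAP 5.4.2 names the analysed variable as days with either symptom type and does not invoke the SAP 5.1 formula. Read literally, it can include days before coincidence. The *or* in SAP 5.2 may offer alternatives rather than equate them, and the table titles do not settle it. This stands: the loss of days is conditional, not established. It does not remove the problem. SAP 5.4.2 counts days during the confirmed event, and SAP 5.1 starts that event at coincidence, so the text does not clearly recover the earlier days and gives no other derivation.

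It can also be said that starting an episode when the case definition is met is defensible. Protocol 3.2.2 fixes when symptoms have resolved but not when the clock starts. That is fair, but the choice still has to be stated. A first-symptom start also needs a way to decide which early symptoms belong to the episode in people with chronic conditions. Protocol 7.3 leaves that separation to the investigator, and the fix can rely on it. A simple span from first symptom to last stop date would include symptom-free days, so it is not the right replacement.

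A reader might infer that the conflict between SAP 5.1 and SAP 5.4.2 causes the loss of symptom days. It does not. The first-symptom rule is limited to the time-to-event analysis, and any loss comes from the SAP 5.1 formula alone.

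**Conclusion.** The inconsistency in time to onset is real. It can give a case counted in the primary VE a negative time in the Cox sensitivity analysis, probably rarely. The symptom-days variable is left undefined between two readings. Under one of them, cases with staggered onset are understated by exactly the lag, and some drop a band. How many is unknown: the 3% to 41% range rests entirely on assumed durations and lags.

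Two stronger readings are not supported. One is that the vaccine's effect on illness duration would be biased in a known direction. The same rule applies to both arms, and nothing in the documents suggests that the lag differs between them; without such a difference, the effect is misclassification and a mis-stated duration. The other is that the main result is at risk. The primary conclusion rests on the exact conditional analysis of case counts (SAP 5.4.1 and 5.4.2), which uses neither duration nor event time. This should be corrected, but it concerns a secondary endpoint and a sensitivity analysis.

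**What to change.** Make two changes to the SAP before unblinding, so that the onset date is not chosen with results in view.

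1. Define a qualifying date as the first day on which the ILI definition is met. Use it for the 14-day eligibility rule and as the event time in the Cox and Kaplan-Meier analyses, and amend the first-symptom sentence in SAP 5.4.2 to agree with SAP 5.1.
2. State in SAP 5.4.2 that the banded variable is the number of days with any respiratory or systemic symptom that the investigator attributes to that ILI episode, counted from the first such symptom. State that the SAP 5.1 episode duration is not used for this endpoint.

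The cost is a few sentences. The SAP's existing rules already require first-symptom, coincidence and symptom stop dates, so the changes should need no new data collection. The band list has to be opened in any case: as written in SAP 5.4.2 and section 11, a value of exactly 21 days belongs to no band.
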